5. STUDY PROCEDURES

Phlebotomy:

Blood will be collected once by a standard venipuncture. Blood will be collected in chemistry tubes (EDTA) and cell preservative tubes (Streck) to be stored in the Canary Center at Stanford biorepository and to be sent to our Boston University collaborators for processing and analysis. A total of 30 mL will be collected in a one-time blood draw. Blood draw will take place within 1 month after the patient has been consented.

¹⁸F-FSPG PET/CT and Integrated Biomarkers for Early Lung Cancer Detection in Patients with Indeterminate Pulmonary Nodules

Nasal Brushing:

Patient will be asked to blow their nose. A small speculum is used to widen the nostril and a tiny brush (the size of a Q tip) is put in through the speculum and rotated for 3 seconds. This brush is then removed, and a second brush is inserted and rotated for 3 seconds. Finally, the speculum and brush are removed from the nose. Nasal brushing will take place within 1 month after the patient has been consented.

¹⁸F-FSPG PET/CT scan:

The patient will be injected with the radiotracer and allowed to rest for about 60 minutes. He/she will then be placed in the PET/CT and a static whole-body scan will be obtained from the vertex of the skull to the mid-thighs, starting at 60 (\pm 10) minutes after radiotracer injection.

6. STUDY CALENDAR

	Visit 1	Within 1 month from Visit 1 (can be Visit 2/3)	Visit 2 or 3*	Visit 3 or 2*	Within 24 to 72 hours after ¹⁸ F-FSPG PET/CT
Informed consent	X				
Nasal Brushing		X			
Blood draw		X			
¹⁸ F-FDG PET/CT			X		
¹⁸ F-FSPG PET/CT				X	
Patient follow-up					X

* &  : PET/CT exams is not specified and may be reversed. PET/CT exams will be scheduled at least 24 hours apart, and no more than 2 weeks apart.

7. COMPENSATION

Study participants will be compensated with a total of \$500 for the time it takes them to complete the study procedures, including time and transportation for the additional visit to the clinic for the PET/CT procedure.

8. ADVERSE EVENTS AND REPORTING PROCEDURES

8.1. Risks and Potential Adverse Events

The risk associated with phlebotomy is small and includes discomfort, a bruise at the point where the blood is taken, redness, infection, and a rare risk of fainting. The risk associated

¹⁸F-FSPG PET/CT and Integrated Biomarkers for Early Lung Cancer Detection in Patients with Indeterminate Pulmonary Nodules

with the nasal brushing procedure is also small and includes minor discomfort and temporary nose bleed.

¹⁸F-FSPG has been administered to over 65 cancer patients world-wide with no adverse events reported. As such, there are no major risks that are known or expected with this radiopharmaceutical. However, general risks to keep in mind include the radiation exposure. The expected radiation exposure of an ¹⁸F-FSPG scan in this study is expected to be similar to or less than that of an ¹⁸F-FDG scan. Other risks to patients are mainly related to the intravenous (IV) injection. Although the risk is small, intravenous injection can cause infection, injection site discomfort, and bruising.

8.2. Adverse Event Reporting

Patients will be contacted for follow up within 24 to 72 hours after the ¹⁸F-FSPG PET/CT, Adverse events will be graded according to CTCAE v5. Both Serious and Non-Serious Adverse Events will be clearly noted in source documentation. The Protocol Director (PD) or designee will assess each Adverse Event (AE) to determine whether it is unexpected according to the Informed Consent, Protocol Document, or Investigator's Brochures, and related to the investigation.

9. REGULATORY CONSIDERATIONS

9.1. Investigational New Drug Application (IND)

This study will be submitted to ¹⁸F-FSPG IND 125516, held by [name] [name].

9.2. Institutional Review of Protocol

The protocol, the proposed informed consent and all forms of participant information related to the study (e.g. advertisements used to recruit participants) will be reviewed and approved by the Stanford IRB and Scientific Review Committee (SRC). Any changes made to the protocol will be submitted as a modification and will be approved by the IRB and SRC prior to implementation. The Protocol Director will disseminate the protocol amendment information to all participating investigators.

Sample management

PET imaging analysis will be performed at Stanford. The blood and nasal samples will be transferred to Boston University for the RNA and DNA sequencing analyses.

9.3. Data Management Plan

We will use OnCore and REDCap for data storage and all paper documents will be stored in a binder in a locked cabinet on Stanford premises.

9.4. Data and Safety Monitoring Plan

During the clinical investigation, the Protocol Director will evaluate the progress of the trial, including periodic assessments of data quality and timeliness, participant recruitment, accrual and retention, participant risk versus benefit, and other factors that can affect study outcome. **The study team meets bi-weekly to review the study conduct and status.**

The Stanford Cancer Institute Data and Safety Monitoring Committee (DSMC) will audit study related activities at least annually in accordance with the DSMC SOP to determine

¹⁸F-FSPG PET/CT and Integrated Biomarkers for Early Lung Cancer Detection in Patients with Indeterminate Pulmonary Nodules

whether the study has been conducted in accordance with the protocol, local standard operating procedures, FDA regulations, and Good Clinical Practice (GCP). This may include review of regulatory binders, case report forms, eligibility checklists, and source documents. In addition, the DSMC will regularly review serious adverse events and protocol deviations associated with the research to ensure the protection of human subjects. Results of DSMC audits will be communicated to the IRB and the appropriate regulatory authorities at the time of continuing review, or in an expedited fashion, as needed.

10. MEASUREMENTS

10.1. Primary Outcome Measure (ClinicalTrials.gov)

The primary outcome is specificity of ¹⁸F-FSPG to discriminate between benign and malignant lung nodules, defined as the proportion of benign cases judged to be benign. With an expected 60 benign cases, an observed 90% specificity would have a 95% confidence interval of 79% to 96%. An observed specificity of 75% would have a confidence interval of 62-85%.

If a patient has multiple nodules, the per-patient assessment will be based on the dominant nodule only, defined as the largest nodule.

Outcome Title: ¹⁸F-FSPG specificity for malignant lung nodules.

Outcome Description: ¹⁸F-FSPG accumulation in lung nodules will be assessed. The observed FSPG specificity will be assessed against a fixed value of 75%.

Timeframe: Up to 5 years.

Safety Issue: No.

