1. OBJECTIVES

1.1. Primary Objective

Comparison of ¹⁸F-FSPG accumulation with ¹⁸F-FDG accumulation to assess whether (4S)-4-(3-¹⁸F-Fluoropropyl)-L-Glutamate (¹⁸F-FSPG) PET is better at discriminating between benign and malignant nodules.

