2.6. Study Design

120 patients with indeterminate lung nodules will be enrolled in the study at Stanford. Blood and nasal brushings will be collected once. The samples from these 120 patients will be part of a bigger cohort of over 900 patients for collaborative data analysis.

All samples will be de-identified before shipment or other data sharing with collaborators takes place. An additional 70 patients who may or may not have smoking history will be imaged at Stanford and analyzed with the other 50 patients enrolled at Stanford.

All 120 patients will be imaged once by ¹⁸F-FSPG PET/CT as part of this open-label, nonrandomized, single-dose explorative study and once by ¹⁸F-FDG PET/CT. PET/CT imaging will be scheduled > 24 hours apart to allow for imaging agent washout, and not more than two weeks apart to allow for optimal image comparison.

Clinical diagnosis (cancer / benign disease) is based on 1) histopathology of biopsy/surgical specimen or 2) surveillance by CT scans for a period of 2 years to confirm that there is no

¹⁸F-FSPG PET/CT and Integrated Biomarkers for Early Lung Cancer Detection in Patients with Indeterminate Pulmonary Nodules

growth of the nodule. All patients without histopathological diagnosis will undergo CT surveillance for a 2-year period by clinical standards.

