PET Imaging: Patients will be imaged by ¹⁸F-FDG PET/CT and ¹⁸F-FSPG PET/CT. Uncorrected maximum lesion intensity (SUV_{max}) along with qualitative measures (absent, minimal, moderate, or high uptake) will be recorded. These data will be analyzed for lung cancer diagnosis using our prospective cohort study design. The person assessing SUV_{max} values and making the decisions about “positive” or “negative” will be blinded to the cancer status of the patient. We will maintain this by keeping the image reader blind to the patient information.

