11.2. Sample Size

Primary outcome: To compare 18F-FSPG PET/CT imaging with 18F-FDG PET/CT imaging for indeterminate lung nodules we will evaluate 120 patients. We estimate that approximately 60 of the patients will be diagnosed with lung cancer after complete diagnostic work-up and ~60 will not have lung cancer. Meta-analysis shows that 18F-FDG has a sensitivity and specificity of 89% and 75% respectively (16). We hypothesize that 18F-FSPG is more specific. With an expected 90% specificity for diagnosis with 18F-FSPG, a sample size of 60 will have 90% power at an alpha-level of 0.05 to demonstrate a significant increase in specificity from a fixed value of 75%.

Secondary outcome: In total the SU2C consortium cohort will be comprised of 930 study participants. Our Stanford group will contribute 120 (60 cases and 60 controls) to the larger sample set. Breakdown of the 930 patients are as follows. For the discovery step, sample size of 100 cases and 100 controls provides 80% power to detect RNA markers with effect sizes of at least 0.52 assuming that we will control the false discovery rate at 10% and 5% of markers are differentially expressed. For the refinement step, 75 cases and 75 controls provides 81% power to detect markers with a ROC AUC of at least 0.63 assuming an alpha level of 0.05. No correction for the multiple hypothesis testing is planned as we will re-evaluate top candidates. The sample size of 190 of each group for model building will support the following:

1. This sample size will be sufficient to include approximately 12 to 20 variables overall between clinical, imaging, ctDNA and gene expression markers based on conventional rules of thumb of 10 to 15 subjects per group per variable;
2. This will allow us to estimate the AUC for each model with a precision of approximately 4.5% (95% CI);
3. Provide 80% power for detecting delta AUCs between models of 0.06 assuming model correlation of 0.6.

For the model testing, 100 subjects in each group will provide AUC precision of ± 0.06 (and a precision of between 0.06 and 0.08 for the sensitivity and specificity), as well as a 80% power to detect differences in AUCs between models of 0.09. IRBs at the other sites have approved the collection of biospecimens and use of clinical / imaging data for this model development and validation work.

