11.4. Criteria for future studies

If ¹⁸F-FSPG PET/CT imaging has a higher specificity for detecting malignant lung nodules compared to ¹⁸F-FDG PET/CT, a larger study will be planned.

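### The only specified FSPG test and the larger-study trigger rest on specificity alone, so a pass cannot separate better discrimination than FDG from a stricter cut-off

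*Combined protocol and SAP*

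**What the plan says.** Section 1.1 sets a comparative question: whether FSPG "PET is better at discriminating between benign and malignant nodules", judged against FDG. Section 11.2 repeats the comparative aim, saying that to compare the two tracers "for indeterminate lung nodules we will evaluate 120 patients", of whom about 60 are expected to have cancer and about 60 not.

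The primary outcome in Section 10.1 is narrower. It is the specificity of FSPG, "defined as the proportion of benign cases judged to be benign", and "The observed FSPG specificity will be assessed against a fixed value of 75" per cent. Sections 11.1 and 11.2 power this one-sample test (90% against 75%, 60 benign cases, 90% power, alpha 0.05). They quote a meta-analytic FDG sensitivity of 89%, but no test uses it.

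Under Section 11.4 a larger study follows if FSPG PET/CT "has a higher specificity for detecting malignant lung nodules compared to" FDG PET/CT. No method or sensitivity condition is given. It is not said whether the FDG value is the trial's own or the fixed 75%.

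The data for a fuller answer are planned. Section 2.6 states "All 120 patients will be imaged once by" FSPG PET/CT and once by FDG PET/CT. Section 10.3 records SUVmax and a four-level visual score. "The person assessing SUV_{max} values and making the decisions about" positive or negative is blinded to cancer status, but no cut-off is given. The same section says "These data will be analyzed for lung cancer diagnosis using our prospective cohort study design", without naming a measure.

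**The concern.** Discrimination concerns both groups: how often benign nodules are called benign and how often malignant ones are called malignant. Specificity alone, at a cut-off that is not fixed, covers one side. It can rise because the tracer separates the groups better, or because the reader demands more uptake before calling a nodule positive. The specified test gives the same result in both cases, because it never looks at a malignant nodule.

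Two things are at stake. The decision in Section 11.4 could rest on sensitivity traded for specificity, although Sections 2.1 and 2.4 justify the work by the need for a sensitive marker with high negative predictive value. And the objective in Section 1.1 would be answered, if at all, by analyses chosen after the data are seen.

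**Working it through.** **1. The plan's own figures.** Inputs from Sections 10.1 and 11.2: n = 60, p0 = 0.75, p1 = 0.90, alpha 0.05 (sidedness not stated).

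- One-sided normal approximation with continuity correction: z = [√60 × (0.15 − 1/120) − 1.645 × √(0.75 × 0.25)] / √(0.90 × 0.10) = (1.097 − 0.712)/0.30 = 1.28, so power is 90.0%. The stated 90% is reproduced.
- Exact binomial, one-sided: reject at 51/60 or more (actual level 0.045); power 92.7%.
- Exact binomial, two-sided: upper rejection at 52/60 or more (upper-tail level 0.021); power 85.8%.
- Clopper-Pearson: 54/60 gives 79.5% to 96.2%, and 45/60 gives 62.1% to 85.3%, matching Section 10.1.

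The arithmetic is sound for the one-sample question.

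**2. What the test does not see.** The pass probability depends only on true specificity. A marker with 90% specificity and 10% sensitivity has a positive likelihood ratio of 0.10/(1 − 0.90) = 1, so its calls carry no diagnostic information. It passes with the same 92.7% or 85.8% as one with 89% sensitivity. This step needs no model.

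**3. Hypothetical illustration: FDG's own ROC curve at a stricter cut-off.** Assume an equal-variance binormal curve through the plan's FDG point.

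- Separation = Φ⁻¹(0.89) + Φ⁻¹(0.75) = 1.2265 + 0.6745 = 1.901.
- Sensitivity at 90% specificity = Φ(1.901 − 1.2816) = Φ(0.619) = 73%.
- Missed cancers among 60: 60 × 0.11 = 6.6 at the original point; 60 × 0.268 = 16.1 at the stricter one.
- The pass probability is that of step 1: 93% or 86%.
- With unequal variances, b being the benign-to-malignant SD ratio, sensitivity = Φ(1.2265 − 0.6071b). For an assumed b from 0.58 to 1.25 this is 81% to 68%.

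**4. Whether another analysis fills the gap.** DeLong's test in Section 10.2 compares an integrated model with a clinical model. Section 2.4 lists the FSPG pilot among the data types for an algorithm, but the model-building text in Section 11.1 develops CT features and compares models, not tracers. No paired FSPG-FDG analysis is named.

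**5. What the planned numbers can support** (60 benign, 60 malignant, two-sided 0.05; correlations and discordance are assumptions).

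- Sensitivity 53/60: 95% CI 77% to 95%.
- Paired specificity, 90% against 75%, exact McNemar: power 90%, 70% and 50% at discordance 15% (the minimum), 20% and 30% (independent reads: 0.90 × 0.25 + 0.10 × 0.75). Half-width 1.96 × √[(discordance − 0.15²)/60] = 9 to 13 points.
- Paired sensitivity, 89% against 73%: power 93% at minimum discordance (16%), 52% with independent reads (32%).
- AUC difference, both near 0.90: Hanley-McNeil SE 0.0293 each; half-width 1.96 × 0.0293 × √[2(1 − r)] = 0.05 (r = 0.6) to 0.07 (r = 0.3).

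**The case against.** The strongest reply is that this is an explorative, open-label study, that success commits the sponsor only to planning a larger one, and that specificity is the natural primary measure because the case for FSPG is lower uptake in benign inflammation. All of that stands, and it is why the primary test should remain.

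It is also fair that the 93% or 86% is essentially the plan's own power. It becomes a misleading pass only if FSPG has FDG's ROC curve and is read more strictly. The documents give no evidence of either, and a reader blinded to cancer status cannot tune individual calls to the diagnosis. Blinding does not fix a cut-off, however.

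A reader might go further and infer that the trial is likely to promote an inferior tracer, or that Table 1 in Section 2.5 already shows FSPG discriminating less well. The documents do not support this. Treating Table 1 as normal gives AUCs of 0.80 for FSPG and 0.86 for FDG, but with 7.52 ± 6.68 that model puts Φ(−7.52/6.68) = 13% of cancers at a negative SUVmax. A log-normal reading reverses the order (0.92 against 0.89), and at 90% specificity FSPG is the more sensitive under both. Table 1 is no evidence against FSPG.

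Finally, paired analyses are not free of conditions. Section 10.3 does not say that the two tracers are read independently, and Section 5 gives acquisition details only for FSPG.

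**Conclusion.** The concern holds as a mismatch between objective and analysis. Section 1.1 asks about discrimination relative to FDG. The specified test and the trigger address specificity alone, and no named analysis brings in the malignant cases. The conclusion that a pass cannot distinguish better discrimination from a stricter cut-off follows from the text and needs no model.

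The size is illustrative. Sensitivity falling from 89% to about 73% with a 93% or 86% chance of passing assumes that FSPG shares FDG's ROC curve, that the curve is equal-variance binormal through a pooled literature point, and that the cut-off lands at 90% specificity. It shows what the rule would permit, not what is expected. Specificity is not the wrong primary outcome, and the sample-size calculation is not wrong. In an exploratory study this is a worthwhile, inexpensive improvement.

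**What to change.** Keep the specificity test as primary. Add to Sections 10 and 11, as secondary analyses with 95% confidence intervals:

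- the paired FSPG-FDG difference in AUC on SUVmax, by DeLong's test (already used in Section 10.2 for another purpose);
- FSPG sensitivity, and its paired difference from FDG in malignant cases;
- the paired specificity difference in benign cases, by exact McNemar test.

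Fix one positivity rule per tracer (an SUVmax value or a level of the visual score) before reference diagnoses are unblinded. Have the same blinded reader assess each tracer without sight of the other, and state how FDG acquisition is kept comparable.

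In Section 11.4, state that the comparator is the trial's own paired FDG result. Add one explicit condition, for example that the FSPG AUC point estimate is not below FDG's, with the sensitivity difference and its interval reported alongside. An explicit condition is preferable to weighing the estimates together, which would leave the decision to judgement after the data are seen.

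The cost is protocol wording, reading discipline and a few analyses, with no new patients or scans. The trigger becomes somewhat harder to meet. If the true AUC gain were 0.05 from an assumed 0.85, the example condition would hold with probability Φ(0.05/0.0387) = 90% to Φ(0.05/0.0296) = 95% (correlation 0.3 to 0.6). If the AUCs were equal it would hold about half the time, by symmetry, so it is a coarse safeguard. The added estimates are imprecise (step 5 of the working) and should be labelled as supporting estimates, not a powered joint criterion.

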10.2. Secondary Outcome Measure (ClinicalTrials.gov)

The secondary outcome is improved performance of an integrated prediction model to discriminate between benign and malignant lung nodules, compared with a clinical prediction model.

Outcome Title: Improved prediction model for lung nodules

Outcome Description: Improved performance is defined as a $p < 0.05$ increase in the C statistic determined using DeLong's test for correlated ROC curves.

Timeframe: Up to 5 years.

Safety Issue: No.

10.3. Measurement Methods

For RNA and DNA sequencing the blood and nasal samples will be transferred to Boston University. PET imaging analysis will be performed at Stanford.

Total RNA-seq of Nasal Brushings: RNA sequencing libraries will be prepared from total RNA samples using Illumina® TruSeq® Stranded Total RNA Library Preparation Kit. The libraries from individual samples will be multiplexed in groups of 4 for cluster generation on

¹⁸F-FSPG PET/CT and Integrated Biomarkers for Early Lung Cancer Detection in Patients with Indeterminate Pulmonary Nodules

the Illumina® cBot® using Illumina® TruSeq® Paired-End Cluster Kit. Each sample will be sequenced on the Illumina® HiSeq® 2500 to generate paired-end 75 nucleotide reads. De-multiplexing and creation of FASTQ files will be performed using Illumina CASAVA software. RNA-Seq reads will be aligned to the human genome (hg19) using STAR, quality metrics will be calculated using RSeQC, and gene and transcript expression levels will be summarized using RSEM and Ensembl annotation. Gene and transcript filtering will be conducted on normalized counts using the mixture model in the SCAN.UPC R package. R software will be used to conduct all further analyses. Batch correction will be done using a modified version of our SCAN algorithm²⁹ that is adapted to work with sequencing counts.

Single Cell RNA-seq of Nasal brushing: Nasal brushings will be subject to Fluorescent Activated Cell Sorting (FACS) (10 markers specific to either immune or epithelial cells) and sorted into single cells. Plates of single cells will be processed for single cell RNA sequencing using the CEL-Seq2 protocol, 75 bp single-end reads (400K/cell), on 200 single cells/sample.

Circulating tumor DNA: ctDNA lung cancer biomarker will be developed using plasma samples available on 380 patients (n = 190 each cases and controls). This biomarker will then be validated on the remaining 200 samples. We will analyze plasma samples using TEC-seq. Tumor WES sequencing will be performed on a subset of training set (n=150) to confirm source of ctDNA. Using the same genomic libraries utilized for TEC-seq, we will also perform whole genome analyses to identify chromosomal abnormalities using the Digital Karyotyping approach. TEC-seq and whole exome seq profile somatic mutations which is not considered genetic.

PET Imaging: Patients will be imaged by ¹⁸F-FDG PET/CT and ¹⁸F-FSPG PET/CT. Uncorrected maximum lesion intensity (SUV_{max}) along with qualitative measures (absent, minimal, moderate, or high uptake) will be recorded. These data will be analyzed for lung cancer diagnosis using our prospective cohort study design. The person assessing SUV_{max} values and making the decisions about “positive” or “negative” will be blinded to the cancer status of the patient. We will maintain this by keeping the image reader blind to the patient information.

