2.5. Preliminary results

[figure not shown]
[figure not shown]

Figure 1. Mutation frequencies in cfDNA of lung cancer patients. The ctDNA mutational frequencies (bars) are similar to previously reported tumor mutation frequencies (dots) from COSMIC for 76 out of 81 genes analyzed ($P > 0.05$ for 76 of 81 genes),

Detection of mutations in circulating tumor DNA. We have used both targeted and whole genome methods (5) to identify genomic alterations in the plasma of healthy individuals and patients with cancer. Most recently, we have used the TEC-seq approach described above to examine plasma specimens from 44 healthy individuals: no mutations were observed in the cancer driver genes analyzed in our panel. We next analyzed plasma samples from lung cancer ($n = 64$), breast cancer ($n = 46$), colorectal cancer ($n = 42$), and ovarian cancer patients ($n = 42$). These untreated patients were largely diagnosed at stage I and II. We found that the concentration of ctDNA in plasma from cancer patients was ~ 29 ng/mL, significantly higher than that observed in healthy individuals ($n = 44$; 7 ng/mL; $P = 0.001$). By TEC-seq, we detected cancer driver mutations in plasma from over half of stage I and II colorectal, ovarian, lung, and breast cancer patients. The affected genes and mutation frequencies in the lung cancer patient plasma was similar to what has previously been reported (Figure 1). On average, 2.1 alterations were observed in each patient with detectable ctDNA, with lung cancers having a higher number of alterations per case. We next evaluated 216 alterations in 100 patients where matched tumor tissue and blood cells were available. Overall, 82 of the 100 patients (82%) had at least one alteration observed in the circulation that was identical to that in the tumor specimen. We therefore expect that the fraction of cancer patients with a ctDNA-detected mutation will increase as the TEC-seq panel is expanded to include more cancer-associated mutations.

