11. STATISTICAL CONSIDERATIONS

11.1. Statistical Design and Data Analysis

Clinical diagnosis is based on 1) histopathology of biopsy/surgical specimen or 2) surveillance by CT scans for a period of 2 years to confirm that there is no growth of the nodule. Meta-analysis shows that ¹⁸F-FDG has a sensitivity and specificity of 89% and 75% respectively (16). We hypothesize that ¹⁸F-FSPG is more specific. With an expected 90% specificity for diagnosis with ¹⁸F-FSPG, a sample size of 60 will have 90% power at an alpha-level of 0.05 to demonstrate a significant increase in specificity from a fixed value of 75%.

Integrated predictions models:

Our biomarker discovery and validation will use samples from 930 patients in the intended use population collected prior to diagnosis; and subsample from all available cancer and non-cancer patients. Through our experience with the NCI Early Detection Research Network (EDRN), we have a detailed plan for biomarker discovery and validation, which is briefly summarized here.

¹⁸F-FSPG PET/CT and Integrated Biomarkers for Early Lung Cancer Detection in Patients with Indeterminate Pulmonary Nodules

Identification of candidate genes from nasal total RNA-seq data: We will initially select 20 to 40 candidate genes that significantly discriminate between cases (n = 100) and controls (n = 100). We will prioritize candidates to: 1) represent cancer-associated gene co-expression patterns, 2) genes whose expression is independent of clinical factors, and genes in significantly enriched functional categories.

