Data Integration: Using a new set of 150 patients (75 cases and 75 controls), we will subset candidate genes and imaging features based on whether they improve (significantly higher ROC curve AUC) clinical lung cancer risk models with the goal of picking no more than 10 genes and 5 imaging features, and prioritizing genes least correlated with imaging features or the ctDNA biomarker. We will next use data from 380 new patients (n = 190 each cases and controls) to train and "lock down" models prior to validation. Model building will use a logistic regression framework (incorporating LASSO and ridge regression) and cross-validation. We will build models stepwise from clinical-variable-only models by adding additional biomarker datatypes (gene expression, imaging, and / or the ctDNA biomarker).

Cross validation will determine the gain in diagnostic performance from each additional datatype, and combinations that do not improve performance will be eliminated. These locked down models will be validated in the remaining samples (n = 200). The primary endpoint will be calculated after every patient has either completed two years of follow up, been diagnosed positive, or died, whichever comes first. The primary endpoint for validation of this prediction model will be replication of improved performance. Exploratory

¹⁸F-FSPG PET/CT and Integrated Biomarkers for Early Lung Cancer Detection in Patients with Indeterminate Pulmonary Nodules

endpoints will determine the range of pre-test probabilities for which the models have potential clinical utility.

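### The ctDNA biomarker is developed in the same 380 patients whose cross-validation decides whether it stays in the model; if it is fitted to case status, its gain is optimistic unless development is repeated in every fold

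*Combined protocol and SAP*

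**What the plan says.** Section 10.3 (Circulating tumor DNA): "ctDNA lung cancer biomarker will be developed using plasma samples available on 380 patients (n = 190 each cases and controls". It continues: "This biomarker will then be validated on the remaining 200 samples". The 380 are called a training set: "Tumor WES sequencing will be performed on a subset of training set (n=150) to confirm source of ctDNA". The inputs are TEC-seq mutations, and from the same libraries "we will also perform whole genome analyses to identify chromosomal abnormalities using the Digital Karyotyping approach". No scoring rule, threshold or model form is given.

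Section 11.1 (Data Integration): "We will next use data from 380 new patients (n = 190 each cases and controls) to train and" lock the models before validation. The method is logistic regression with LASSO, ridge and cross-validation. Datatypes (gene expression, imaging, the ctDNA biomarker) are added one after another to a clinical model. The cross-validated gain decides which combinations survive, and the locked models go to the remaining 200 patients. In an earlier step with 150 other patients, genes are preferred if they correlate little with imaging features or with the ctDNA biomarker.

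Section 10.2 makes the improvement over the clinical model, by DeLong's test at p < 0.05, the secondary outcome. Section 11.1 also says of the whole programme: "we have a detailed plan for biomarker discovery and validation, which is briefly summarized here".

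**The concern.** Cross-validation measures a gain honestly only if everything learned from the outcome is learned again inside each fold. Suppose the ctDNA score is fitted to case status in all 380 and then enters the cross-validation as a finished variable. Each held-out fold has then already helped to build the score it is meant to test. The ctDNA gain comes out too large, a score that does not help is kept more often, and a useful score gets too much weight.

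The plan avoids this for the other datatypes: genes are chosen in a separate 200 and narrowed in a separate 150, and imaging features are narrowed in that 150. ctDNA has no separate step. At stake are the choice of datatypes and the weights in the locked model that goes into the single validation test.

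**Working it through.** **1. Are the two sets of 380 the same?**

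| Step | Patients | ctDNA work described? |
|---|---|---|
| Gene discovery (11.1) | 100 + 100 = 200 | no |
| Refinement (11.1) | 75 + 75 = 150 | no, but the ctDNA biomarker is used as a ranking criterion |
| Model training (11.1), ctDNA development (10.3) | 190 + 190 = 380 | yes |
| Validation (10.3, 11.1) | 200 | yes |

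200 + 150 + 380 + 200 = 930, the cohort total in 11.2. A second, separate 380 does not fit. ctDNA is described for 380 + 200 = 580 patients and not for the other 930 − 580 = 350.

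**2. The plan's own yardstick.** Section 11.2 gives the 380-patient step 80% power for an AUC difference of 0.06 at correlation 0.6. I use the Hanley-McNeil variance with 190 per group, two-sided 0.05, and an assumed baseline AUC of 0.75 (none is stated):
- SE(0.75) = 0.0249 and SE(0.81) = 0.0222.
- SE of the difference = √(0.0249² + 0.0222² − 2 × 0.6 × 0.0249 × 0.0222) = 0.0212.
- Power = Φ(0.06/0.0212 − 1.96) = 81%. It runs from 69% to 96% for baseline AUC 0.65 to 0.85.

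The stated figure reproduces. Any optimism should be read against 0.06.

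**3. Size of the optimism, by simulation.** All settings are assumptions, because the algorithm is not stated:
- 190 cases and 190 controls; clinical AUC 0.76 (the preliminary figure in 2.5); 81 independent binary genes (the number in 2.5).
- Control positivity 8%, the upper 95% limit for 0 of 44 healthy people, in whom "no mutations were observed in the cancer driver genes analyzed in our panel": 1 − 0.025^(1/44) = 8.0%. Healthy people are not nodule controls.
- Case positivity 50% (informative), 20% (weak) or 8% (uninformative).
- LASSO score; 10-fold cross-validation; ctDNA kept if its gain is above 0; true gain taken in 4000 new subjects; 150 runs per scenario.

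Each cell shows the 1-SE penalty, then the minimum-deviance penalty.

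| ctDNA | Un-nested gain | Its true gain | Kept without benefit: un-nested | Kept without benefit: nested |
|---|---|---|---|---|
| Informative | +0.089, +0.100 | +0.058, +0.060 | – | – |
| Weak | +0.010, +0.026 | 0.000, −0.004 | 23%, 57% | 6%, 9% |
| Uninformative | +0.005, +0.012 | −0.002, −0.004 | 16%, 37% | 5%, 7% |

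- Excess for the informative marker: 0.089 − 0.058 = 0.031 and 0.100 − 0.060 = 0.040. Nested, the estimates are +0.052 and +0.057 against true +0.056 and +0.060.
- A ridge score gives +0.110 against +0.076 true (excess 0.034), and +0.077 nested. A forced ten-best-genes score gives +0.064 against +0.049 (excess 0.015).
- A pre-set any-mutation call shows no optimism: +0.081 estimated, +0.082 true.
- Pure-noise ridge scores at 10% prevalence give −0.001, +0.009, +0.021 and +0.086 for 1, 10, 20 and 81 features. Nested, they give −0.001 to −0.003.

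**4. Power in the 200 (100 + 100, DeLong), informative marker.**
- ctDNA the only useful addition: 73% and 71% un-nested, 84% and 85% nested. The paired losses are 10 and 14 points (SE 0.6 and 0.7).
- Mechanism, minimum-deviance penalty, 100 further runs without the keep rule: the true gain is +0.060 both ways, but the DeLong SE is 0.0245 un-nested and 0.0206 nested. Φ(0.060/0.0245 − 1.96) = 69%; Φ(0.060/0.0206 − 1.96) = 83%. The loss comes from over-weighting, not from poorer discrimination.
- Other datatypes already adding 0.09 AUC: about 98% against 99%, a loss of 1 to 2 points. In the same setting a weak marker gives 88% against 91%, and 81% against 92%.

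**5. Order of steps.** The ranking in the 150 needs ctDNA values there. Section 10.3 describes ctDNA only in the later 380 and the remaining 200. A fitted biomarker would not yet exist at that step. A pre-set one would exist as a rule, but no measurements to apply it to are described.

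**The case against.** Nothing in the plan says that the score is frozen on all 380 before cross-validation, and 11.1 calls itself a summary. A fold rule may exist elsewhere, in which case one sentence settles the matter. The ctDNA biomarker enters as one datatype, and 2.5 reports mutations in over half of early-stage cancers and none in 44 healthy people, so a simple pre-set call is conceivable and would bring no optimism. The magnitudes depend on an assumed algorithm. The 10 to 14 points require ctDNA to be the only useful addition, whereas 2.5 reports gains from nasal genes and from imaging. All of this stands, and it limits the size of the point. It does not remove it: developing a biomarker from 190 cases and 190 controls most naturally means fitting it to case status, and the document gives no fold rule.

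A reader might infer three stronger things that the documents do not support:
- That the validation is contaminated. It is not: the 200 are separate patients and the models are locked first.
- That the locked model discriminates worse. For an informative marker its AUC in new patients is nearly the same.
- That a pre-set rule would by itself make the 150-patient criterion workable. It would not, because no ctDNA measurement is described for those patients.

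**Conclusion.** The point holds, conditionally. The same 380 patients serve to develop the ctDNA biomarker and to judge its contribution. If the biomarker is fitted to case status and development is not nested, its training gain is overstated. With penalised scores the illustrative excess is about 0.03 to 0.04 AUC for an informative marker, against the 0.06 the step is designed to detect, and a marker of no benefit is retained more often. A pre-set rule or a score with very few fitted parameters gives almost no excess.

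The harm is confined to the training step and the locked model: an over-weighted or useless ctDNA term, and some loss of power for the secondary outcome. With an informative marker the loss is 10 to 14 points if ctDNA is the only useful addition and 1 to 2 points if other datatypes already add 0.09. The validation test, its type I error and the primary outcome are untouched.

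The 150-patient ranking on ctDNA cannot be applied as written, whichever form the biomarker takes. This does not depend on the simulation. That the two sets of 380 coincide is inferred from the counts, which leave no other split.

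**What to change.** In 10.3 and in Data Integration (11.1), state the form of the ctDNA biomarker and when it is fixed. Then choose one:
- Pre-specify a ctDNA rule that is not fitted to outcome, and correct the wording in 10.3 that has it developed in the 380.
- If it is fitted, repeat all ctDNA development (feature selection, penalty, threshold) inside every cross-validation fold, fit the integrated weights on out-of-fold ctDNA scores, and refit on all 380 only for the locked model.

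In either case, delete the ctDNA biomarker from the gene-ranking criterion in the 150, or apply that criterion inside the folds of the 380. Measuring ctDNA in the 150 would need extra assays and is not proposed.

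Cost: wording and analysis code, with no new samples or sequencing. The downsides are more computation, a smaller stated training gain, and a slightly useful score dropped a little more often. In the weak scenario, a score with a true gain above 0.005 was dropped in 2% to 4% of nested runs and in 0% of un-nested runs.
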